At the time of enrollment, those randomized to intervention 1 will receive written hygiene instructions and a form to document outcomes, such as missed school or work. Those randomized to (or placed in) intervention 2 will receive a "kit", which will include a bucket for measuring the water, two cups to be used for measuring bleach, Clorox bleach, mupirocin ointment, double sided q-tips for application of mupirocin, hygiene instructions, as well as a form to document outcomes. Participants will also receive a link to an online video demonstrating the accurate process for preparing the diluted bleach bath and administering the mupirocin. (www.youtube.com/watch?v=3RbtyLT071M&feature=youtu.be) For each intervention arm, the above materials will be sent via mail after enrollment or provided in person by a research assistant.

Outcomes Measures

The patient-centered outcomes we plan to measure are summarized below.

The results of PAB sessions performed during aim 1 of this study will further inform some of the patient-centered outcomes measures.

Recurrence of SSTI

 Percent of participants with recurrence of skin and soft tissue infection by parental report at 6 weeks, 6 months and 12 months.
Repeat surgery

 Percent of participants with repeat incision and drainage procedure by parental report at 6 weeks, 6 months and 12 months.
Adherence to intervention

 Participant adherence to intervention measured on a 5 point scale by parental report at 6 weeks Household adherence measured on a 5 point scale by parental report at 6 weeks Have you tried anything outside the protocol to reduce the risk of MRSA recurrence? If yes, then what? (6 weeks)
Side effects
Percent of participants with side effects from intervention by parental report at 6 weeks and 6 months.
Participant time committed to intervention
Estimated weekly time to adhere to intervention by parental report at 6 weeks
Quality of Life

 Participants' quality of life measured by parent-proxy report (or youth tool) of the PedsQL 4.0 (Pediatric Quality of Life Inventory) at recruitment, 6 weeks, 6 months, and 12 months. Impact on free time measured on a 5 point scale by participant (age\geq13) and parental report at 6 weeks
Impact on school attendance

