An RA will contact a parent of participants by phone at approximately 6 weeks after study randomization. The RA will ask parents of participants about adherence to interventions. The RA will initiate the conversations by saying “we are very interested to know what people think about the protocol”. For any of the interventions experienced (hygiene measures, mupirocin to nose, and bleach bath) participants will then be asked to report adherence. Adherence will be reported on a 5 point scale for child and other family members: We followed the instructions as recommended – always, sometimes, never.

For the purpose of analysis “always”, “never omitted more than one time/dose/bath in a row” and “never omitted more than one day/week in a row” will be considered adherent to treatment.

RAs will also ask: “Have you tried anything outside the protocol to reduce the risk of MRSA recurrence? If yes, then what?” This should capture any patients in the control arm who may be using decolonization regimens outside their designed protocol.

Side effects

An RA will contact a parent of participants by phone at approximately 6 weeks after randomization. The RA will ask parents of participants about side effects to interventions, for example: “Did any family member experience side-effects from the intervention? All parents will also be asked: “Dry skin and irritation in the nose or runny nose are sometimes reported in families, have any of your family members experienced those symptoms?”

Participant time committed to intervention

An RA will contact a parent of participants by phone at approximately 6 weeks after randomization. If participant report that they adhere to the protocol, the RA will ask parents to estimate the amount of time (in hours) per week they estimate the intervention took for all family members combined.

Quality of Life

Impact on quality of life will be measured by the use of Peds QL, Pediatric Quality of Life Inventory.²² The Peds QL was developed to measure health-related quality of life (HRQOL) in healthy children and adolescents and those with acute and chronic health conditions. The RA will administer the 23-item parent proxy report of the Pediatric Quality of Life Inventory in person or by phone at recruitment and at recruitment, and over the phone at approximately 6 weeks, 6 months, and 12 months. Participants 13 and older will be able to give self-report.

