We will also assess the impact of the protocol on free time. RAs will ask participants (13yrs and older) “How much has the diagnosis of MRSA impacted your ability to do the things you like to do in your free time?”

Impact on school attendance

An RA will contact a parent of participants by phone at approximately 6 weeks, 6 months and 12 months. Parents of participants will be asked whether their child have missed any school days due to MRSA SSTI. Parents will be asked about number of school days missed.

Impact on parents' work attendance

An RA will contact a parent of participants by phone at approximately 6 weeks, 6 months and 12 months. Parents of participants will be asked whether they have missed any workdays due to their child's or their own MRSA SSTI. Parents will be asked about number of work days missed.

Medical data that cannot be collected directly from the parent of the patient, such as infection site, size of boil, location of reoccurrence may be collected via review of medical record.

Study Timeline

	Year 1				Year 2				Year 3			
	Qtr 1	Qtr 2	Qtr 3	Qtr 4	Qtr 1	Qtr 2	Qtr 3	Qtr 4	Qtr 1	Qtr 2	Qtr 3	Qtr 4
Aim 1 – PAB Sessions												
Aim 2 – Recruitment												
Aim 2 – Data Collection												
Statistical Analysis												
Manuscript Preparation												

6.0 Reporting of Adverse Events or Unanticipated Problems Involving Risk to Participants or Others

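### As scripted, the free-time question asks about the MRSA diagnosis rather than the protocol, and the side-effect questions record a family rather than a participant, so neither yields the outcome listed

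*Combined protocol and SAP*

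**What the plan says.** All of this is in section 5.0 of the combined protocol and SAP.

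**Free time.** Under Outcomes Measures, Quality of Life, the plan lists "Impact on free time measured on a 5 point scale by participant" for those aged 13 or older, "and parental report at 6 weeks". In the later Quality of Life text the purpose is "We will also assess the impact of the protocol on free time". The next sentence gives the item, put to participants 13 and older: "How much has the diagnosis of MRSA impacted your ability to do the things you like to do in your free time". No wording for parents follows.

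**Side effects.** Outcomes Measures lists "Percent of participants with side effects from intervention by parental report at 6 weeks and 6 months". The Side effects text describes a call at about 6 weeks. It gives an example question, "Did any family member experience side-effects from the intervention", and then a prompt for all parents asking whether any family members had dry skin, nasal irritation or a runny nose. Neither asks which person was affected.

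**Adherence, for contrast.** The same list has two separate lines: "Participant adherence to intervention measured on a 5 point scale by parental report at 6 weeks" and "Household adherence measured on a 5 point scale by parental report at 6 weeks".

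**The concern.** The research assistants will ask what the script says. If the script asks something other than the listed outcome, that outcome cannot be recovered at analysis.

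For free time, the stated purpose and the item differ in what they measure. Section 1.0 gives learning how burdensome the prevention strategies are as part of the rationale, and Sub Aim 2c in section 2.0 makes the burden of decolonization an aim. An item about the diagnosis does not isolate that burden. If decolonization eased the disease but took up time, the two effects could offset in one answer, and similar scores in the two arms would be hard to interpret.

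For side effects, the unit differs. A yes for any family member is a household result. It rises with the number of people in the household and is at least as frequent as the average per-person result. Presented as a percentage of participants, it would overstate how often a treated person has side effects.

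**Working it through.** The plan states no figure for either outcome, so there is nothing to reproduce. The check compares the outcome list with the collection text, followed by two illustrations.

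**1. Free time: what is measured and who answers**

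| | Outcomes Measures | Quality of Life text |
|---|---|---|
| Construct | impact on free time | purpose: the protocol; item: the diagnosis |
| Respondent | age 13 or older, and parent | age 13 or older |
| Scale and time | 5 points, 6 weeks | not restated |

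Section 3.0 requires a culture-confirmed MRSA abscess, so every index child has the diagnosis the item asks about. The arms can still be compared, but the answer carries both burdens. Eligibility starts at 3 months, so without a parent item no free-time question is described for ages 3 months to 12 years.

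**2. What would be lost if no parent were asked (illustration)**

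- The item is asked at 6 weeks. Section 8.0 gives 95 enrolled and 20% drop-out by then. Reading 95 as per group, 95 × 0.8 × 0.9 × 0.9 = 61.6 at 12 months, which fits the target of 59 per group. At 6 weeks, 95 × 0.8 = 76 per arm.
- Assume ages are spread evenly. The share aged 13 or older is (18 − 13)/(18 − 0.25) = 28% if eligibility ends at the 18th birthday, or (19 − 13)/(19 − 0.25) = 32% if 18-year-olds are included. That is about 21 to 24 of 76 per arm.
- For a two-sample t-test (two-sided 0.05, 80% power), the smallest detectable difference is 0.46 SD at 76 per arm, 0.83 SD at 24 and 0.89 SD at 21.
- With an assumed share of 20% to 50%, the number is about 15 to 38 per arm, and the detectable difference 1.06 to 0.65 SD.

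The plan claims no power for this 5-point item, and the 76-per-arm figure treats youth and parent answers as one measure. The figures show scale only.

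**3. Side effects: the unit**

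- Listed: percentage of participants. Asked: any family member, in both questions given.
- Section 3.0 lists household members among eligible participants, so participants may mean more than index children. That does not help: one yes from a family does not say how many were affected, or who.
- Section 5.0 directs the interventions to household members who consent. The prompted symptom question is not limited to them or to effects of the intervention, so it can count people who did not receive it. The example question is limited to effects of the intervention, so this applies mainly to the prompt.
- The list has 6 weeks and 6 months. The Side effects text describes only 6 weeks; the general data-collection text names side effects among the phone-interview topics without tying them to a contact.

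**4. Size of the unit mismatch (illustration)**

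The documents give no side-effect risk, household size or within-household correlation, so all three are assumed. With independent members, the chance that at least one of k is affected is 1 − (1 − p)^k. With intra-household correlation ρ (beta-binomial), let s = (1 − ρ)/ρ and b = (1 − p)s. The chance is then 1 minus the product of (b + i)/(s + i) for i = 0 to k − 1.

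- p = 0.10, k = 4, independent: 1 − 0.9⁴ = 0.344.
- p = 0.10, k = 4, ρ = 0.2: 0.271.
- p = 0.10, k = 4, ρ = 0.5 (s = 1, b = 0.9): 1 − (0.9/1)(1.9/2)(2.9/3)(3.9/4) = 0.194.
- p = 0.10, k from 2 to 6, ρ from 0 to 0.5: from 0.145 (k = 2, ρ = 0.5) to 0.469 (k = 6, independent).
- 5% against 15% per person, k = 4: 0.185 against 0.478 if independent (29 points); 0.101 against 0.281 at ρ = 0.5 (18 points). The per-person difference is 10 points.

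**The case against.** The best defence is that section 5.0 outlines the procedures and is not the full instrument. The data form is not in the documents, and the open side-effect question is marked as an example. Parental report of free time is in the outcome list, so silence in the later text does not show that it was dropped. Household members may count as participants, so asking about the family is not in itself the wrong unit. Burden is also captured by weekly hours and adherence, and PedsQL is collected as well.

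Much of this stands, and it limits the point. A reader might infer that parents will not be asked about free time; the documents support only that no parent item is described. A reader might infer that the investigators will report household answers as participant percentages; the documents do not say so. A reader might also infer that the free-time item cannot compare the arms; it can, but it cannot separate the two burdens.

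Three things remain. The purpose sentence and the free-time item conflict in adjacent sentences. The prompt put to all parents is not marked as an example and is also at family level. And no record by person is described for side effects, although the plan separates child and family for adherence.

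**Conclusion.** The point holds as a mismatch between listed outcomes and scripted questions. Followed as written, the free-time item does not isolate protocol burden, no parent free-time item is described, and the side-effect questions cannot give a percentage of participants.

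The extent of mixing in the free-time answer is unknown. The side-effect gap is sized only under assumed inputs: a 10% per-person risk appears as 19% to 34% of households of four. Household size should be balanced in expectation between randomized households, so the unit affects the level and size of a difference more than its direction.

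It would go too far to conclude that the trial cannot assess burden, since weekly hours and adherence are still collected, or that its main result is compromised. These are secondary outcomes, and the recurrence outcome and its sample size do not depend on them. The change is worth making before data collection because a family yes/no does not show afterwards who was affected.

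**What to change.** **Free time.** Ask how much the steps the family was asked to follow have affected the ability to do things they like in their free time. Put it to youth 13 and older and to the parent, on the 5-point scale at 6 weeks, and report the two respondents separately. The steps differ by arm, and the analysis text should say so. Keep the diagnosis item as a second question if it is wanted.

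**Side effects.** At the 6-week and 6-month contacts, ask first about the index child and then about other consented household members. Report index-child and household percentages separately, and state which people the word participants covers in the listed outcome.

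**Cost.** Edits to the interview script and the REDCap form. The parent is already on the call. Free time gains a parent question (and one more if the diagnosis item is kept), and the side-effect question is split in two at two contacts. Calls become slightly longer; the documents give no call length from which to say by how much.

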In this study, we intend to compare two therapies for MRSA SSTI (abscess surgery and hygiene education compared to abscess surgery and hygiene education followed by decolonization) to determine which is the more effective treatment for MRSA SSTI. We will focus on patient-centered outcomes as described by the families of MRSA infected patients. Such outcomes are likely to include quality of life, side effects, and school and work attendance. The hypothesis is that treatment with decolonization will decrease the rate of SSTI recurrence and improve overall patient-centered outcomes. The rationale is that negative outcomes such as recurrence may be avoided through the use of readily available prevention strategies, however, it is important to determine how burdensome those prevention strategies are for patients and families.

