
 Participants' school attendance by parental report at 6 weeks, 6 months and 12 months
Impact on parents' work attendance

 Assessment of parents' work attendance by self report at 6 weeks, 6 months and 12 months
Other Patient Centered Outcomes

 Participant's level of pain and discomfort at incision site via NRS at enrollment and 6 weeks. Participant's level of knowledge on what MRSA is and how to prevent its recurrence at enrollment, 6 weeks, 6 months, and 12 months. Additional measures as suggested by Aim 1

Data Collection and Study Tools

In order to evaluate the outcomes identified above, data will be collected by RAs in person or by phone at enrollment, and through phone interviews at approximately 6 weeks, 6 months and 12 months as time allows within the study period. RAs will be trained to perform phone interviews to assess recurrence, adherence, side effects, quality of life and school/work attendance. When requested by the participant, data collection tools/questions may be mailed via US post and/or emailed via secure link to REDCap. For all practical outcomes, such as missed school and work, participants will have forms to help them document these outcomes to aid in recollection at follow up.

The data collection for specific outcomes is outlined below:

Recurrence of skin and soft tissue infection

An RA will contact a parent of participants by phone at approximately 6 weeks, 6 months and 12 months. Participants will be asked whether they have had a recurrence of MRSA SSTI since the previous contact. If the answer is yes, they will also be asked if and where medical care was sought, and if any interventions (surgery, antibiotics) were needed. In cases for which antibiotics were prescribed, the name of antibiotics and duration of course will be recorded.

Repeat surgery

In a continuation of the questioning as shown above, an RA will contact a parent of participants by phone at approximately 6 weeks, 6 months and 12 months. They will be asked whether participants needed another incision and drainage procedure for MRSA SSTI in the same or another body location. If the answer is yes, they will also be asked in what facility that was done and whether antibiotics was prescribed or not. In the cases for which antibiotics were prescribed, the name of antibiotics and duration of course will be recorded.

Adherence to intervention

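### School and work attendance are listed without a cause, but the interview asks only about days blamed on MRSA SSTI; days lost to the decolonization regimen are not asked for

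*Combined protocol and SAP*

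**What the plan says.** Attendance is named without a cause in several places. Sub Aim 2b (Section 2.0) compares the interventions on school attendance, and the introduction to Aim 2 in Section 5.0 speaks of school absence. The Outcomes Measures list in Section 5.0 has "Participants' school attendance by parental report at 6 weeks, 6 months and 12 months" and "Assessment of parents' work attendance by self report at 6 weeks, 6 months and 12 months".

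The data-collection text later in Section 5.0 attaches a cause. For school: "Parents of participants will be asked whether their child have missed any school days due to MRSA SSTI". For work: "Parents of participants will be asked whether they have missed any workdays due to their child's or their own MRSA SSTI". Each is followed by a count question that does not restate the cause: "Parents will be asked about number of school days missed" and "Parents will be asked about number of work days missed".

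Hygiene-arm families receive "a form to document outcomes, such as missed school or work", again with no cause stated. The decolonization kit also holds an outcome form.

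Regimen burden is itself a question of the trial. Section 1.0 says that "it is important to determine how burdensome those prevention strategies are for patients and families", and Sub Aim 2c is devoted to burden and preferences. Section 8.0 describes no analysis of the attendance outcomes.

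**The concern.** The label promises a comparison of attendance. The question delivers a comparison of absence that a parent attributes to MRSA infection. These differ in two ways that matter between arms.

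First, only one arm is assigned bleach baths and mupirocin, and these go to every consented household member. The question counts absences that decolonization may prevent and does not ask about absences that it may cause.

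Second, the parent decides the cause and knows the arm. A shift in what parents blame on MRSA would look like a shift in attendance.

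At stake is whether Sub Aim 2b can report the net effect on attendance. Days that are never asked for cannot be recovered at analysis.

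**Working it through.** **No figure to reproduce.** The documents give no expected days, variance, effect size or power for attendance. The only sample size (59 per group, Section 8.0) is for recurrence and is unaffected.

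**Do other items fill the gap?** All are in Section 5.0.
- Side effects: asks whether symptoms occurred, not whether days were lost.
- Time committed: asks for hours per week, and only from families who report adherence. Families who stopped are not asked.
- Free time: introduced as the impact of the protocol, but the question concerns the diagnosis of MRSA.
- PedsQL: a quality-of-life score, not a count of days missed for a given cause.

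**Does the count question fill the gap?** There are three readings.
1. It inherits the cause from the question before it (the natural reading). Regimen days are then not requested.
2. It is put only to those who answered yes, but covers all days. Other-cause days are then counted only for families with an MRSA absence, a group that differs by arm if treatment works.
3. It is put to everyone for all days. That is a different outcome from the question that precedes it.

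The text does not say which applies.

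**Direction of error.** Let C and D be true mean infection days per child in the control and decolonization arms, and r the mean regimen days in the decolonization arm. Let q be the share of regimen days that parents report as MRSA days, and aC and aD the ratio of reported to true infection days in each arm.

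- True difference = D + r − C
- Observed difference = aD·D + q·r − aC·C
- Bias = observed − true = −(1−q)·r + (aD−1)·D − (aC−1)·C

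A negative bias favors decolonization. The first term is the omission. For q between 0 and 1 it is zero or negative. The other two terms are attribution error and can take either sign.

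The values below are assumptions chosen to show direction, not size, with C = 2 and D = 1 throughout:

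| r | q | aC | aD | True | Observed | Bias |
|---|---|---|---|---|---|---|
| 0 | 0 | 1 | 1 | −1 | 1 − 2 = −1 | 0 |
| 0.5 | 0 | 1 | 1 | −0.5 | 1 − 2 = −1 | −0.5 |
| 1.5 | 0 | 1 | 1 | +0.5 | 1 − 2 = −1 | −1.5 |
| 0.5 | 1 | 1 | 1 | −0.5 | 1 + 0.5 − 2 = −0.5 | 0 |
| 0.5 | 0 | 1 | 0.8 | −0.5 | 0.8 − 2 = −1.2 | −0.7 |
| 0.5 | 0 | 0.7 | 1 | −0.5 | 1 − 1.4 = −0.4 | +0.1 |
| 0.1 | 0 | 0.8 | 1 | −0.9 | 1 − 1.6 = −0.6 | +0.3 |
| 0.5 | 0.5 | 1 | 1.3 | −0.5 | 1.3 + 0.25 − 2 = −0.45 | +0.05 |

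The first four rows have exact attribution of infection days, and the bias there is zero or favors decolonization. The last four add misattribution, and the net bias goes both ways.

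**The case against.** **The cause-specific question may be the intended outcome.** The list is a summary and the later text is its working definition. Days missed because of MRSA is a legitimate measure for a recurrence-prevention trial and is less noisy than all-cause days. This stands as far as it goes: such an outcome is sound if labeled so, but here it is not.

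**The regimen may cost no whole days.** It is two 15-minute soaks a week for 6 weeks and ointment for ten days. The prompted effects are dry skin and nasal symptoms, and Section 6.0 does not anticipate adverse events. This stands. Any such days would also fall almost entirely before the 6-week call.

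**Burden is measured elsewhere.** Side effects and weekly hours are collected. True, but neither yields days missed.

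**Cause-specific questions still depend on unmasked parents.** This stands too, and a prompt that makes sense in one arm only would invite extra reports there. It is the reason for identical wording in both arms and for an all-cause total.

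A reader might infer more than the text supports in three respects:
- *That the comparison can err only in favor of decolonization.* This holds for the omission alone. Attribution error can outweigh it, as the table shows.
- *That regimen days are excluded.* They are not asked for. Neither the count questions nor the described form restates a cause, and nothing tells a parent how to classify such a day, so some may be counted.
- *That the uncounted days would offset a known share of the benefit.* The documents give neither days per recurrence nor days lost to the regimen, so any such share would rest on invented inputs.

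**Conclusion.** The point holds as a mismatch between the listed outcome and the question asked. As written, the plan measures absence attributed to MRSA SSTI by parents who know their arm, and does not ask for absence caused by the regimen. It therefore cannot support a net comparison of attendance under Sub Aim 2b.

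The omission alone is neutral or favors decolonization, provided regimen-related absence is not more common in the control arm. That proviso is needed because the adherence interview allows for control families using decolonization outside the protocol. Unmasked attribution adds error of either sign. The total size is unknown, and the omission may be near zero. The outcome is one of several patient-centered measures, and the recurrence comparison is not touched. The change is still worth making because it is cheap and the missing answers cannot be collected reliably afterward.

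**What to change.** 1. At each call, ask for the total number of school days and parent workdays missed for any reason, then how many of these were due to a skin infection.
2. At the 6-week call, in both arms and in the same words, also ask how many were due to measures taken to prevent MRSA or to their side effects.
3. Put matching lines on the family form in both arms.
4. Report by arm all-cause days and the sum of infection-related and prevention-related days. Label the existing measure *MRSA-attributed absence* in the outcome list.

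The cost is slightly longer calls and a revised form. All-cause counts will be noisier, and the cause-specific counts will still rest on the judgment of unmasked parents.

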Oversight for the conduct of the study will be provided by the study PI, [name], with input and advice from his mentorship panel. He will take primary responsibility for overseeing data collection and verification and review of cumulative adverse events. While adverse events are not anticipated, a process has been established for continuous review of data and patient safety. The PI and his study team (PResNet RA and PResNet Study Coordinator) will conduct quarterly review meetings of the data. Other members will be included in these meetings at the discretion of the PI. Quarterly meeting summaries will include the number of patients recruited, rate of recruitment refusal, and subject attrition. Additionally the research team will report (1) all causes of mortality and (2) morbidity (hospitalizations, ER visits, and other injuries/problems resulting from the study protocol). Any adverse events occurring will be documented and reported according to Human Research Protection Program (HRPP) at Indiana University policies and procedures. This (de-identified) summary may be submitted to the Patient Advisory Panel (PAB) of the Patient Engagement Core. Cumulative adverse events and study progress summary will be communicated to the IRB at the time of continuing review.

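### Section 6.0 promises reports of deaths, hospitalizations and ER visits, but no scheduled interview asks about them in the same way in both arms, so the counts may be incomplete and unequal

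*Combined protocol and SAP*

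**What the plan says.** **The duty (Section 6.0).** The investigator and study team "will conduct quarterly review meetings of the data". The research team is also to report "all causes of mortality and (2) morbidity (hospitalizations, ER visits, and other injuries/problems resulting from the study protocol". On handling, the section says: "Any adverse events occurring will be documented and reported according to Human Research Protection Program (HRPP) at Indiana University policies and procedures". It does not say how events are to be found.

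**The collection (Section 5.0, Data Collection and Study Tools).** Follow-up is at about 6 weeks, 6 months and 12 months. The topics are listed once: "RAs will be trained to perform phone interviews to assess recurrence, adherence, side effects, quality of life and school/work attendance". The items that bear on safety are these:

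- Recurrence: "Participants will be asked whether they have had a recurrence of MRSA SSTI since the previous contact". Care use hangs on that answer: "If the answer is yes, they will also be asked if and where medical care was sought, and if any interventions (surgery, antibiotics) were needed".
- Repeat surgery: "They will be asked whether participants needed another incision and drainage procedure for MRSA SSTI in the same or another body location".
- School and work: days missed because of MRSA SSTI.
- Side effects: an example of an open question, covering any family member, about side effects of the intervention. All parents also get a prompt that begins "Dry skin and irritation in the nose or runny nose are sometimes reported in families".

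The outcome table in Section 5.0 schedules side effects at 6 weeks and 6 months. The Side effects procedure text gives about 6 weeks only. The Aim 2 heading in the same section names side effects among the outcomes on which the two strategies are compared.

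**The concern.** A reporting duty is only as good as the question that feeds it. Here the reported categories and the interview items do not line up, and the items that come closest can behave differently in the two arms. One opens only after a recurrence, which is the outcome decolonization is meant to change. The other asks the parent to judge cause, when one arm has been given a kit of bleach and mupirocin and the other written hygiene advice.

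The setting makes this matter. The kit goes to homes where Section 3.0 allows household members from 3 months of age, and the regimen is aimed at all consented members. Section 3.0 excludes people with known sensitivity to bleach or mupirocin, so the hazard is recognized. Yet no item prompts for an allergic, eye or breathing reaction or for accidental exposure to a product. A low count could then be read as reassurance at the quarterly review, or in a final weighing of burden against benefit, when it partly reflects what was asked.

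**Working it through.** The documents give no safety-event rate, so there is no safety figure to reproduce. The check sets the duty beside the items, then sizes the one conditional route that can be sized.

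**Step 1. Duty against items**

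| Section 5.0 item | Asked when | Condition | General question on death, hospital or ER? |
|---|---|---|---|
| Recurrence | 6 weeks, 6 and 12 months | MRSA SSTI | No |
| Care sought | same | only after a reported recurrence | No |
| Repeat surgery | same | incision and drainage for MRSA SSTI | No |
| School and work days | same | due to MRSA SSTI | No |
| Open side-effect question | see step 3 | parent attributes it to the intervention | No |
| Dry-skin and nasal prompt | see step 3 | none; all parents | No |
| Medical record review | optional | examples are infection details | No |

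Section 7.0 adds one voluntary route: families who stop therapy are encouraged to contact the research assistant.

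**Step 2. Reach of the care-sought question**

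Inputs from Section 8.0: 50% recurrence with hygiene education; a 50% relative reduction, so 0.50 × 0.5 = 0.25 with decolonization; 95 enrolled; dropout of 20% at 6 weeks and 10% at each of the two later contacts.

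Check that 50% and 25% are the rates the plan used. With two-sided alpha 0.05, 80% power and the mean proportion (0.50 + 0.25)/2 = 0.375:

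2 × (1.960 + 0.842)² × 0.375 × 0.625 / 0.25² = 58.9, so 59 per group, as stated.

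Section 8.0 does not say outright that 95 is per group. Two groups of 59 make 118, which 95 in total could not supply, so 95 is taken as per group.

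- Dropouts multiply: 95 × 0.8 × 0.9 × 0.9 = 61.6 reached at 12 months. With a recurrence: 61.6 × 0.50 = 30.8 (hygiene) and 61.6 × 0.25 = 15.4 (decolonization).
- Dropouts add: 95 × (1 − 0.2 − 0.1 − 0.1) = 57. With a recurrence: 57 × 0.50 = 28.5 and 57 × 0.25 = 14.25.

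So about 29-31 hygiene-arm families and 14-15 decolonization-arm families would be asked where care was sought. The ratio is 0.50/0.25 = 2 whatever the enrolment, provided dropout is equal in the arms.

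**Step 3. Timing of the side-effect questions**

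- Outcome table: 6 weeks and 6 months.
- Side effects procedure text: about 6 weeks.
- General data-collection paragraph: lists side effects as a topic without assigning it to a contact.

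Neither specific text places side effects at 12 months, and the two disagree about 6 months.

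**Step 4. Direction**

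The recurrence-triggered question opens more often in the hygiene arm. The attribution-based question is likely to draw more answers from the arm that received the kit. The two pull in opposite directions, so the net imbalance cannot be signed from the documents.

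**The case against.** The strongest case on the other side has five parts.

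- **The duty may be narrower than it looks.** A reader might infer that all hospitalizations and ER visits must be reported. The text is all-cause explicitly only for mortality. The qualifier closing the morbidity list may cover the whole list or only its last item. If it covers the whole list, an attribution-based question is closer to what is required. This stands, and the ambiguity needs settling. It does not remove the gap: all-cause death has no question under either reading.
- **The side-effect interview is a real route.** It is open, covers any family member and is worded as an example. A parent could mention an ER visit for a rash in reply. The bleach soaks run 6 weeks and mupirocin ten days, so the 6-week call covers the planned exposure. This stands, but the item still asks for attribution and does not ask about hospital or ER use.
- **There are other routes.** These are optional record review, contact by families who stop therapy, and institutional adverse-event policy, which is not in the documents. A child's death would probably emerge when a parent is reached, though not in families lost to follow-up. This stands as a reason for caution about size. As cited, the policy governs events that have occurred; the protocol describes no elicitation under it.
- **One item is even-handed.** The dry-skin and nasal prompt goes to all parents. This stands for those symptoms only.
- **No by-arm table of deaths, hospitalizations or ER visits is planned.** Section 6.0 describes summaries and cumulative reports. This stands, but side effects are a named comparison under Aim 2.

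**Conclusion.** The concern holds in this form: Section 6.0 sets a duty to report deaths and morbidity, and Section 5.0 provides no uniform, arm-independent way to collect them. Counts may be incomplete and may differ between arms for reasons of ascertainment. The one part that can be sized is the care-sought question, which would reach about twice as many hygiene-arm families. That rests on the plan's 50% and 25% rates and on equal dropout; the counts of 29-31 and 14-15 also need 95 per arm.

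Three stronger readings are not supported:

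- **That the counts will be falsely low.** No background rate is given and other routes exist, so undercounting is a risk, not a demonstrated result.
- **That nothing is asked from week 6 to week 52.** The outcome table schedules side effects at 6 months, so a 46-week gap follows only if the procedure text overrides it.
- **That zero-event confidence bounds measure the problem.** Such bounds assume full capture. Adjusting them would need a capture rate that the documents do not give.

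This is a cheap improvement to safety ascertainment. It does not challenge the recurrence analysis.

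**What to change.** 1. At the existing 6-week, 6-month and 12-month contacts, ask both arms one short block in the same words, not conditional on recurrence or attribution. Since the last contact, has any enrolled household member died, been hospitalized, visited an ER, had a skin, eye, breathing or allergic reaction, or had accidental exposure to a study product?
2. Record which member was affected. Record relatedness afterwards, as a separate field.
3. Report these events by arm, with related events as a subset.
4. State in Section 6.0 whether the qualifier at the end of the morbidity list limits hospitalizations and ER visits or only the other injuries and problems.
5. Reconcile the side-effect timing between the outcome table and the Side effects procedure text in Section 5.0.

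Cost: a few more minutes per call, one additional REDCap form, an IRB amendment, and more unrelated events to log. No new contacts or staff are needed.
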